10.5 URGENT SAFETY MEASURES

The Sponsor/Sponsor's designee or investigator may take appropriate urgent safety measures (USMs) in order to protect the subject of a clinical trial against any immediate hazard to their health or safety. This includes procedures taken to protect subjects from pandemics or infections that pose serious risk to human health.

USMs may be taken without prior authorization from the competent authority.

Should the site initiate a USM, the investigator must inform the Sponsor or Sponsor's designee immediately either by:

Primary Contact	Secondary Contact
Refer to your country-specific fax number in the Study Manual for the Sponsor designee's Pharmacovigilance team contact. Email: [contact]	Refer to your country-specific contact information in the Study Manual for the Sponsor Medical Monitor Email: [contact] [contact]

The notification must include:

- the date of the USM,
- who took the decision, and
- why action was taken

The Sponsor or Sponsor's designee will then notify the applicable regulatory authority(ies) (eg, Medicines and Healthcare Products Regulatory Agency) and the applicable RECs within the required timeframes (eg, 3 days of USM initiation in the UK).

10.6 PREGNANCY REPORTING

Female subjects who become pregnant during the trial or treatment period must have study treatment stopped immediately.

The investigator must make every effort to try and ensure that a subject or a partner of a subject does not become pregnant during the trial and for 6 months after their final dose of SRA737. This should be done as part of the consent process by explaining clearly to the subject the potential dangers of becoming pregnant and also providing each subject with

information about appropriate medically approved contraception. Two forms of medically approved contraception must be used as described in Appendix 4.

However, if a subject or a partner of a subject does become pregnant, the reporting procedures below must be followed.

Any pregnancy occurring in a subject or a subject's partner during treatment with an IMP or occurring within 6 months of last IMP administration must be reported to the Sponsor or Sponsor designee's Pharmacovigilance Department within 24 hours of the site staff becoming aware, using a Pregnancy Notification Report (provided in the Investigator Trial File [ITF]).

It is the investigator's responsibility to obtain consent for follow-up from the subject or subject's partner. The Sponsor or Sponsor designee's Pharmacovigilance Department will follow-up all pregnancies for the pregnancy outcome via the investigator, using a Pregnancy Follow-up Report.

The investigator must ensure that all subjects are aware at the start of a clinical trial of the importance of reporting all pregnancies (in themselves and their partners) that occur whilst being treated with the IMP and occurring up to 6 months after the last IMP administration. The investigator should offer counseling to the subject and/or the partner, and discuss the risks of continuing with the pregnancy and the possible effects on the fetus. Monitoring of the subject and the baby should continue until the conclusion of the pregnancy, if the subject or subject's partner provides consent.

11 DATA ANALYSIS AND STATISTICAL CONSIDERATIONS

As this is an open label, first-in-human study, data trends will be reviewed in real time. There will also be 2 planned interim reviews on the accumulating data. These are not formal statistical interims and the reviews are conducted in part for patient safety. There will be no adjustment to significance levels for reviews of the accumulating data during the trial. The planned reviews will occur at the following time points:

- At the completion of patient follow-up for the last subject enrolled at the end of the dose escalation
- At the completion of the expansion cohort for each indication

The final analysis will be conducted after one of the following conditions is met:

- The trial is terminated early
- The end of trial as defined in Section 12.5 has been reached

Additional analysis may be conducted for regulatory, publication, or decision making purposes.

11.1 ANALYSIS POPULATIONS

11.1.1 SAFETY EVALUABLE POPULATON

All enrolled subjects who receive at least 1 dose of SRA737 will be evaluable for safety.

11.1.2 RESPONSE EVALUABLE POPULATON

All enrolled subjects who have measurable disease, receive at least 75% of 1 cycle of study medication, and have a baseline assessment of disease plus at least 1 post-baseline disease assessment will be evaluable for response. All subjects who were enrolled into one of the 6 indication-specific expansion cohorts will be evaluable for response if they have measurable, prospectively-selected genetically-defined tumors as specified in Section 4, received at least 75% of 1 cycle of study medication, have a baseline assessment of disease and at least 1 post-baseline disease assessment.

In addition, subjects who have measurable disease and receive at least 75% of 1 cycle of study but develop disease progression, intolerable toxicity, or death prior to the post-baseline assessment will also be considered evaluable and will be classified as nonresponders.

11.1.3 PHARMACOKINETICS EVALUABLE POPULATON

All subjects who receive at least 1 dose of SRA737 and provide at least 1 evaluable PK concentration will be included in the PK analysis. Concentrations will be eligible for inclusion into PK analyses if the subject receives the full dose and does not vomit within 4-hours postdose.

11.1.4 PHARMACOKINETICS/CORRECTED QT INTERVAL EVALUABLE POPULATON

All enrolled subjects who receive at least 1 dose of SRA737 and for whom adequate QTc and ECG data are available will be evaluable for PK/QTc analyses.

11.1.5 PHARMACODYNAMICS EVALUABLE POPULATION

All enrolled subjects who receive at least 1 dose of SRA737 who have evaluable data for each specific PDn assessment will be evaluable for PDn.

11.2 STATISTICAL ANALYSES

11.2.1 PRESENTATION OF DATA

Data will be presented in a descriptive fashion. Variables will be analyzed to determine whether the criteria for the trial conduct are met. This will include a description of subjects who did not meet all the eligibility criteria, an assessment of protocol deviations, IMP accountability and other data that impact on the general conduct of the trial.

Baseline characteristics will be summarized for all enrolled subjects.

Treatment administration will be described for all cycles. Dose administration, dose modifications or delays and the duration of therapy will be described.

11.2.2 SAFETY

Safety data will be collected from the date of written informed consent. Safety variables will be summarized by descriptive statistics. Laboratory variables will be described using the NCI-CTCAE v4.03. The MTD for each schedule tested, if reached, and the RP2D and schedule will be described.

Treatment-emergent AEs will be reported for each dose level and coded using a current version of the MedDRA thesaurus, presented as tables of incidence of AEs by body system and by worst severity grade observed. Additional tables will be prepared to summarize incidence of AEs reported as related and unrelated events.

11.2.3 EFFICACY ANALYSES

The analysis of all efficacy endpoints will be based on the Response Evaluable Population.

Efficacy endpoints will be evaluated using RECIST v1.1 criteria, or for subjects with NHL, the revised IWG criteria ([Cheson 2007](#)), or for subjects with mCRPC, a composite response rate defined as any one of the following ([Scher 2016](#)):

- Best response based on RECIST v1.1
- PSA decrease of $\geq 50\%$

- CTC count conversion

Absolute values for PSA and CTCs will be recorded at baseline and response will be analyzed based on percentage of change.

Descriptive analyses of the distribution of ORR, DCR, DOR, TTR, TTP, PFS per RECIST v1.1, the revised IWG criteria, or a composite of any one of the following:

A) Response based on RECIST v1.1; B) PSA decrease of $\geq 50\%$; or C) CTC count conversion, as applicable, and OS will be prepared.

The ORR will be summarized using binomial proportions and confidence intervals computed by the method of Wilson. The examples below display the CI estimates for response within each indication-specific group of approximately 20 enrolled to an expansion cohort. i.e. at the 95% CI, 0 of 20 responses observed excludes an ORR of 16%.

Numerator	Denominator	Proportion	Lower	Upper
0	20	0	0	0.161
1	20	0.05	0.009	0.236
2	20	0.10	0.028	0.301
3	20	0.15	0.052	0.360
4	20	0.20	0.081	0.416
5	20	0.25	0.112	0.469
6	20	0.30	0.145	0.519
7	20	0.35	0.181	0.567
8	20	0.40	0.219	0.613
9	20	0.45	0.258	0.658
10	20	0.50	0.299	0.701
11	20	0.55	0.342	0.742
12	20	0.60	0.387	0.781
13	20	0.65	0.433	0.819
14	20	0.70	0.481	0.855
15	20	0.75	0.531	0.888
16	20	0.80	0.584	0.919
17	20	0.85	0.640	0.948
18	20	0.90	0.699	0.972
19	20	0.95	0.764	0.991
20	20	1	0.839	1

The distribution of DOR, in the subset of subjects responding will be summarized using Tukey's five number summary, including the minimum, mean, median, maximum and

standard deviation. Time to response will be summarized using Tukeys' five number summary. The ORR and DCR will be summarized for the Response Evaluable Population and for important subgroups including, but not limited to, genetically-defined subjects selected by the next-generation sequencing (NGS) techniques, either retrospectively or prospectively, subjects enrolled into one of the indication-specific cohort expansions, and subjects defined by dose level to which they were enrolled. Additional subgroups of interest may also be identified, and the ORR will be estimated, as described in the Statistical Analysis Plan.

Duration of response is defined as the time from first evidence of PR or better to disease progression or death. Analysis of DOR will be performed using the Kaplan-Meier method. Medians and other quartiles for DOR will be estimated in addition to the corresponding 2-sided 95% confidence intervals.

Statistical analysis of OS will include data from all subjects, and data from subjects alive at the end of the study will be included in the Kaplan Meier Analysis as a censored observation with censoring at the last available visit where survival status was ascertained. Progression free survival will include data from all subjects including subjects who did not progress and were alive at the end of the study. Censoring rules will be defined in the SAP. The statistical analysis of OS and PFS will be prepared using the Kaplan Meier estimator, and variance estimated using the Greenwood Estimator.

All other efficacy variables will be further defined in the statistical analysis plan.

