4.2 SUBJECT SELECTION CRITERIA

The subject must fulfil the eligibility criteria (listed in Sections 4.2.1 and Section 4.2.2).

4.2.1 *INCLUSION CRITERIA*

Dose Escalation Phase and Cohort Expansion Phase

1. Written (signed and dated) informed consent and capable of co-operating with treatment and follow up.
- 2a. For subjects in the Dose Escalation Phase: any locally advanced or metastatic, histologically or cytologically proven solid tumor or NHL, that is relapsed after or progressing despite conventional treatment for which no conventional therapy is considered appropriate by the investigator or is declined by the subject.
- 2b. For subjects in the Cohort Expansion Phase: locally advanced or metastatic, histologically or cytologically proven malignancy of the types specified in inclusion criterion 10, for which no other conventional therapy is considered appropriate by the investigator or has been declined by the subject.
3. Life expectancy of at least 12 weeks.
4. World Health Organization (WHO) performance status of 0–1 (Appendix 1).
5. Hematological and biochemical indices within the ranges shown below, measured within one week prior to the subject receiving their first dose of investigational medicinal product (IMP).

Laboratory Test	Lower acceptable limit
Hemoglobin (Hb)	≥ 90 g/L
Absolute neutrophil count	$\geq 1.5 \times 10^9$ /L
Platelet count	$\geq 100 \times 10^9$ /L
Bilirubin	$\leq 1.5 \times$ upper limit of normal (ULN) unless due to Gilbert's syndrome in which case up to $3 \times$ ULN is permissible
Alanine aminotransferase and/or aspartate aminotransferase and Alkaline Phosphatase	$\leq 2.5 \times$ ULN unless raised due to tumor in which case up to $5 \times$ ULN is permissible
Serum Creatinine	$\leq 1.5 \times$ ULN

6. Attained the age of 18 years at the time consent is given.
7. Subjects must have archival tumor tissue available for tumor profiling or accessible tumor and willingness to consent to a biopsy for the collection of tumor tissue. Refer to Section 7.1.1 for more details.

Cohort Expansion Phase

8. Subjects must have measurable disease (per Response Evaluation Criteria in Solid Tumors, version 1.1 [RECIST v1.1]) or, for mCRPC, evaluable disease per any of the following:
 - a. Measurable disease per RECIST v1.1;
 - b. Increasing prostate specific antigen (PSA, see PCWG – Appendix 7); or
 - c. Circulating tumor cell (CTC) count of 5 or more cells per 7.5ml of blood.

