- When archival material was collected more than 18 months ago, the ability to collect fresh tumor tissue should be discussed with the sponsor.
- Suitable archival tumor tissue is defined as $\geq 40 \mu\text{m}$ tissue, of which a minimum of 20% is of malignant origin, on at least 10 and up to 20 unstained slides or in an FFPE block, plus one original (not recut) H&E slide.
- If results from a previously performed determination of tumor genetics are already available for a subject, the sponsor or sponsor's designee must review and approve that data as being sufficient, based on both the type of assay used and the spectrum of genetic information available, to support enrollment without prospective confirmation by this study's central laboratory. For CRC patients, this could include MSI (high status). In cases where the data are approved as sufficient to support enrollment, archival or fresh tumor tissue must still be submitted for retrospective testing by the Central Laboratory after study entry, as noted in Section 7.2.1.

The following must be performed/obtained **within 28 days before** the subject receives their first dose of SRA737:

- Demographic details
- Medical history including current diagnosis, prior treatment, concomitant conditions/diseases, previous cancers (if appropriate), baseline signs and symptoms, and concomitant treatment
- Radiological disease assessments appropriate to the subject's disease must be performed. These may include, but are not limited to: radiological measurements (chest computerized tomography [CT] scan of the liver, abdomen or pelvis, MRI, x-ray; and/or a bone scan). Scans may be collected for potential central review.
 - Imaging should include all areas of known, suspected, or likely sites of disease.

Note: Radiological measurements should in general be conducted within 35 days of C1D1, and thus, should be repeated when the interval is > 35 days due to a delay in start of C1D1, or for any other reason.

- Echocardiogram (ECHO)
- ECG (locally-read)
 - QTcF is to be calculated according to the following formula:
Fridericia's formula: $QT / (RR)^{0.33}$
[Observed QT interval divided by cube root of RR interval]
- Laboratory tests (blood samples):
 - CTCs for mCRPC subjects only (Performed via CellSearch CTC Test)

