- Urinalysis including glucose, protein and blood: Day 1 of each cycle (may be performed up to 72 hours prior to the first dose of each cycle)

- Blood sample for additional exploratory analyses (such as mutational burden): Cycles 3 and 6, Day 1 predose
- ctDNA for exploratory analyses (from a subset of up to 33 subjects): Cycle 3, Day 1 predose
- CTCs for mCRPC subjects only: End of every 4 weeks \pm 1 week
- Serum tumor markers (if applicable, eg, CA-125 for ovarian cancer, PSA for prostate cancer, CEA for colorectal cancer, CA19-9 for pancreatic cancer, AFP for liver and other cancers, and others as clinically indicated): repeated every 4 weeks \pm 1 week after Cycle 1 Day 1)
- Intensive PK schedule:

Intensive PK Assessments	
Continuous schedule	
• C1 Days 1, 8, and 15: Predose• C1 Day 22: Predose, 1, 2, 4, 6, 8, 12, and 24 hours postdose. For subjects in the Expansion Cohorts, the 12-hour time point may be omitted with Sponsor's approval
	Subsequent cycles, Day 1: Predose
Alternate dosing schedules	
• C1 Day 1: Predose• PK will also be collected on Cycle 1 Day 8 or at a day at the end of the first week's dosing as determined by the Sponsor in consultation with the investigator. 
Time points: Predose, 1, 2, 4, 6, 8, 12, and 24 hours postdose. For subjects in the Expansion Cohorts, the 12-hour time point may be omitted with Sponsor's approval

	Subsequent cycles, Day 1: Predose
Note: The Sponsor may reduce or eliminate the requirement for PK sampling once sufficient data to evaluate the PK of SRA737 have been collected and analyzed. If this occurs, the modified requirements will be documented by an update to the Laboratory Manual.	

- Repeat of clinical assessments (if applicable) performed at baseline: This must be repeated at the end of every 4 weeks (\pm 1 week) after Cycle 1 Day 1. Refer to Section 9.
- Repeat of radiological assessments performed at baseline: Radiological assessments must be repeated every 8 weeks (\pm 1 week) after Cycle 1 Day 1. Subjects with bone metastases being followed by bone scans will have scans every 8 weeks (\pm 1 week) for the first 6 months and then every 16 weeks (\pm 2 weeks) thereafter. Assessment may be discontinued if PD was shown on a previous scan. Refer to Section 9.

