9.2 TIMING AND TYPE OF TUMOR ASSESSMENTS

A thorough clinical and radiological evaluation of the malignancy, as judged appropriate by the investigator, and consistent with the protocol, must be performed before a subject receives their first dose of SRA737. The same methods that detect evaluable lesions at baseline must be used to follow these lesions throughout the trial. Imaging based evaluation is preferred to evaluation by clinical examination when both methods have been used to assess the antitumor effect of a treatment.

All radiological assessments must be performed within **4** weeks before starting treatment with SRA737. The interval between the last anti-cancer therapy and these measurements should be at least 4 weeks when possible. All clinical measurements and serum tumor markers that may be utilized to assess response must be performed within **1** week prior to the first dose of SRA737.

The determination of CR and PR requires confirmation by a subsequent assessment at least 4 weeks after the original determination. Stable Disease (SD) determination requires that the relevant criteria be met at least once, a minimum of 6 weeks after study entry.

Copies of any radiological assessments must be available for external independent review if requested by the Sponsor or Sponsor's designee.

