### 11.1.6. Response Criteria for mCRPC Subjects

In addition to the RECIST criteria, response for subjects with mCRPC will also be evaluated by prostate specific antigen (PSA) and Circulating Tumor Cell (CTC). The PSA and CTC data will be presented in listings for mCRPC subjects to facilitate the review of the responses.

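### The protocol's mCRPC composite accepts one unrepeated PSA fall or one undefined CTC conversion as a response, while the protocol body and SAP require CR and PR to be confirmed

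*Protocol*

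**What the plan says.** Protocol 11.2.3, like the synopsis, evaluates mCRPC subjects by "a composite response rate defined as any one of the following": RECIST v1.1 response, a PSA decrease of at least 50%, or "CTC count conversion". It gives no repeat sample or minimum duration for the PSA and CTC parts, and no start or end threshold for conversion. The same section adds that PSA and CTC response will be analysed as percentage change, which is a different kind of rule.

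The only CTC threshold in the documents is 5 cells. It is one of three alternative entry routes for mCRPC in inclusion criterion 8 ("Circulating tumor cell (CTC) count of 5 or more cells per 7.5ml of blood") and recurs in Protocol 9.1 under measurement of disease.

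For RECIST, Protocol 9.2 states: "The determination of CR and PR requires confirmation by a subsequent assessment at least 4 weeks after the original determination". Protocol 9.3 repeats this, and SAP 11.1.1 and its Table 3 build confirmation into the derived response. Protocol Appendix 2, section 2.4.3, says that confirmation is not required in this trial.

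Protocol 7.2.2 schedules "CTCs for mCRPC subjects only: End of every 4 weeks", with PSA at the same interval and scans every 8 weeks.

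SAP 11.1.6 says "response for subjects with mCRPC will also be evaluated by prostate specific antigen (PSA) and Circulating Tumor Cell (CTC"), but provides only listings. The one response table in SAP 16.1 is best overall response per RECIST 1.1. SAP section 13, on changes from the protocol, does not mention the composite.

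**The concern.** A rule that accepts any one of three events has a false-positive rate at least as high as that of its noisiest part. Here the two laboratory parts are read about twice as often as scans and need no repeat, while the imaging part must be seen twice. The protocol does not trust a single PSA value at entry: Appendix 7 requires a sequence of rising values. It asks for no such repeat when PSA declares a response.

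A CTC result is a small count. If conversion means crossing 5 downwards, a subject whose true level sits a little above 5 will sometimes read below it with no change in disease. ORR is listed under a primary objective, and the cohort has about 20 subjects, so one or two such subjects would visibly move an mCRPC composite rate. That rate would also not be like for like with the confirmed RECIST rates of the other cohorts.

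**Working it through.** **1. The plan's own figure.** Wilson 95% interval, n = 20, z = 1.96. For 0/20 the upper limit is z²/(n + z²) = 3.8416/23.8416 = 0.161, as in the table in Protocol 11.2.3. For 1/20 the interval is 0.009 to 0.236, also as tabulated. One false responder therefore moves the estimate from 0% (upper limit 16.1%) to 5% (upper limit 23.6%).

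**2. CTC noise.** From the documents: a cut-off of 5 and one read every 4 weeks, so two reads by week 8 and three by week 12. Assumed: conversion means going from 5 or more to below 5; counts are Poisson and independent between visits; the true mean does not change. The true means are illustrative.

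Let q = P(count ≤ 4). At least one of two reads below 5 has probability 1 − (1 − q)². Both reads below 5 has probability q².

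| True mean | q | At least one of two | Both |
|---|---|---|---|
| 6 | 0.2851 | 48.9% | 8.1% |
| 8 | 0.0996 | 18.9% | 1.0% |
| 10 | 0.0293 | 5.8% | 0.1% |
| 15 | 0.0009 | 0.2% | about 0 |

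Example at mean 6: 1 − 0.7149² = 0.489, and 0.2851² = 0.081.

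With three reads, a single low count gives 63.5%, 27.0% and 8.5% at means 6, 8 and 10. Two consecutive low counts give 13.9%, 1.9% and 0.2%.

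**3. Sensitivity.** With variance twice the mean (negative binomial), q rises to 37.7%, 19.4% and 9.0% at means 6, 8 and 10. Conditioning instead on the observed baseline (flat prior on the true mean), at least one of two reads is below 5 in 53.8% of subjects at a baseline of 5 and 10.6% at 10. Both reads are below 5 in 21.7% and 1.3%. At a baseline of 20 or more, even the single-read rule gives about 0.1% or less.

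**4. Cohort scale (illustration only).** If 5 of 20 subjects had a true mean of 8, two reads would give 5 × 0.189 = 0.95 expected false converters, and 1 − 0.8107⁵ = 65% chance of at least one. With the repeat rule these become 5 × 0.0099 = 0.05 and 4.9%.

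**5. PSA noise.** Log-normal within-subject variation is assumed. A chance fall of at least 50% in either of two reads occurs in 0.1% of subjects at a CV of 15%, 1.3% at 20% and 8.4% at 30%. When both reads must show it, the figures are about 0, 0.1% and 1.2%.

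**6. Sample spacing.** Nominal spacing is 28 days with a window of ±1 week, so consecutive samples can be 28 − 7 − 7 = 14 days apart. A repeat rule tied simply to the next sample would not guarantee 3 weeks.

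**The case against.** The strongest reply is that the planned analysis never computes this composite. SAP ORR is confirmed RECIST, and PSA and CTC appear only in listings. A reader might infer that the tabulated mCRPC ORR will be inflated by counting noise. The documents do not support that, because a chance low CTC count cannot enter that table. What stands is narrower: the protocol's endpoint remains as written, SAP 11.1.6 still says response will be evaluated by PSA and CTC without a rule for doing so, and section 13 is silent.

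A reader might also infer that criterion 8 fills the analysis with subjects chosen for a count just above 5. It does not. CTC is one of three entry routes, and the Response Evaluable Population (Protocol 11.1.2, SAP 8.2) requires measurable disease, so subjects entering on CTC alone fall outside it as written. The exposed group is subjects with measurable disease whose CTC baseline happens to be near 5.

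The reading of conversion as crossing 5 is an inference. The composite cites published working-group recommendations that may define the term, but the plan does not reproduce a definition. The confirmation contrast is not uniform either, given Appendix 2.

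Six reads at a constant true mean of 6 would give 1 − 0.7149⁶ = 87%. That is a poor headline: it needs about 6 months of stable counts, and disease assessments stop at progression. Rising counts under progression would lower all these figures. Finally, the analyses are descriptive and no decision threshold depends on this rate.

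**Conclusion.** The point holds as a defect of definition with a conditional size. The protocol composite requires no repeat for PSA or CTC and does not say what CTC conversion is. The protocol body and the SAP do require confirmation for CR and PR, and Appendix 2 contradicts them.

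Under the assumptions stated, the single-read CTC rule is unreliable for true means of about 5 to 10 and harmless at about 15 or more. A second read removes most of the error. PSA contributes much less, about 1% over two reads at an assumed CV of 20%. The documents give no CTC distribution, so the number of subjects affected cannot be fixed, and no bias in the SAP's RECIST table is shown. The gap is still worth closing, because it concerns an endpoint under a primary objective and leaves the review of listed values without a rule.

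**What to change.** In the synopsis, Protocol 11.2.3 and SAP 11.1.6:

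- Define CTC conversion by its start threshold, its end threshold and the baseline sample used, and reconcile this with the percentage-change sentence. Name the baseline explicitly. CTCs are scheduled at Screening and before the first dose, but Protocol 7.2.1 lets the second be skipped if it was done in the preceding 3 days, so two pre-treatment counts are not guaranteed.
- Count a PSA fall of at least 50%, or a CTC conversion, as a response only if it is repeated at the first later sample taken at least 3 weeks after.
- Assess conversion only in subjects at or above the start threshold at baseline.
- Show the RECIST, PSA and CTC components separately beside any composite.
- Either tabulate the confirmed composite or record its removal in SAP section 13.

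Also reconcile Appendix 2 section 2.4.3 with Protocol 9.2, 9.3 and SAP 11.1.1.

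The cost is wording and a little more programming; the 4-weekly samples are already scheduled. The downside is a somewhat lower mCRPC response rate.
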